### 7.3.5 Serious Adverse Event Reporting

All serious adverse events (SAEs) that occur from randomization through thirty days after the last dose of study medication must be reported or if the patient is pregnant, 6 weeks following delivery.

The site PI will report the SAE by completing and signing the Serious Adverse Event Report Form [available in the “Study Forms” section of the FRIEND website], and then emailing the document in PDF format to [[contact]](mailto:[contact]). Subjects will be identified by study number only. No other identifying information will be included on the form. The site PI must determine and record on the SAE form whether the SAE is unanticipated or anticipated, and if it is related, possibly related, or unrelated to participation in the research. The site coordinator will enter the information into the DCC database. The DCC will inform the sIRB within 24 hours of after knowledge of a SAE.

The Safety Surveillance team, consisting of the DCC and lead PI of the protocol, will analyze the SAE to determine if it meets the criteria listed in the OHRP 45CFR46 and/or FDA 21CFR312.32 & 3.14.80.

These determinations will dictate timeframes for sites’ submission to the DCC, and the DCC’s submission to the DSMB (Table 2):

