#### 4.3.3 Study Summary

Recruitment and Prescreening: see Section 5 descriptions following.

Screening visit (anytime in cycle 1):

1. Obtain informed, signed consent.
2. Complete medical/gynecological/menstrual history and physical exam of female study participant.
  - Vital signs, height, weight, hip and abdominal circumference, BMI
  - Pap smear if necessary per current ACOG time-frame guidelines
  - Standard pelvic and breast exam conducted by physician or within past 12 months
3. Perform radiological exams.
  - Pelvic ultrasound measuring uterine and ovarian characteristics or within past 3 months
4. Laboratory tests: EGCG and metabolites, liver function, folate, estrogen levels, genetics sample collection and urine pregnancy test.
5. Dispense Green Tea extract and educate on dietary restrictions while taking Green Tea extract and with the importance of taking food. All patients to start Green Tea extract at this visit.
6. Contraception education. Patients will be counseled to use non-hormonal double-barrier method: a male/female condom plus spermicidal agents, cervical cap, diaphragm or sponge.
7. Concomitant medication collection.

Visit 1 (Day 1-5):

Patient will be seen on menstrual cycle day  $3 \pm 2$  days for clomiphene citrate/letrozole initiation visit

1. Vital signs and weight.
2. Laboratory tests: EGCG levels over 8 hours (0.5,1,2,4,6,8), liver function, folate, estrogen level, and urine pregnancy testing.
3. Concomitant medication collection and pill counts of EGCG.
4. Randomization and dispensation of clomiphene citrate/letrozole.
5. Contraception education. Patients will be counseled to use non-hormonal double-barrier method: a male/female condom plus spermicidal agents, cervical cap, diaphragm or sponge.

Visit 2 (day 8-10):

Patient will return several days after final clomiphene citrate/letrozole administration

1. Vital signs and weight.
2. Laboratory tests: EGCG levels over 8 hours (0.5,1,2,4,6,8), liver function, folate, estrogen level and urine pregnancy testing.

3. Concomitant medication collection and pill counts of EGCG and clomiphene citrate or letrozole as appropriate.
4. Contraception education. Patients will be counseled to use non-hormonal double-barrier method: a male/female condom plus spermicidal agents, cervical cap, diaphragm or sponge.

Visit 3 (day 14-16):

1. Pelvic ultrasound via a transvaginal probe or transabdominal transducer evaluation of endometrial thickness and ovarian characteristics.

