### *7.3.3 Time Period and Frequency for Event Assessment and Follow-up*

The occurrence of an AE or serious adverse event (SAE) may come to the attention of study personnel during study visits and interviews of a study participant presenting for medical care, or upon review by a study monitor.

All AEs including local and systemic reactions not meeting the criteria for SAEs will be captured on the appropriate case report form (CRF). Information to be collected includes event description, time of onset, clinician's assessment of severity, relationship to study product (assessed only by those with the training and authority to make a diagnosis), and time of resolution/stabilization of the event. All AEs occurring while on study must be documented appropriately regardless of relationship. All AEs will be followed to adequate resolution.

Any medical condition that is present at the time that the participant is screened will be considered as baseline and not reported as an AE. However, if the study participant's condition deteriorates at any time during the study, it will be recorded as an AE.

Changes in the severity of an AE will be documented to allow an assessment of the duration of the event at each level of severity to be performed. AEs characterized as intermittent require documentation of onset and duration of each episode.

Site personnel will record all reportable events with start dates occurring any time after informed consent is obtained until 7 (for non-serious AEs) or 30 days (for SAEs) after the last day of study participation. At each study visit, the investigator will inquire about the occurrence of AE/SAEs since the last visit. Events will be followed for outcome information until resolution or stabilization.

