### *7.3.4 Adverse Event Reporting*

Adverse events deemed non-serious will be recorded throughout study participation from the start of study drug through one week after the last dose of study medication and reported to the DCC. Non-serious adverse events will be reported to the DSMB quarterly.

Supervising Institutional Review Boards (IRBs) will be notified by local investigators of adverse events occurring at their institution according to their reporting requirements. Investigators also will notify the medical monitor and DCC within 24 hours after knowledge of a death or of an event that is life-threatening, that results in hospitalization or prolongation of hospitalization, or that involves a persistent or significant disability or incapacity. Study staff will collect information regarding the treatment provided, outcome, and presumed relationship to study, and a narrative description of the event. The study staff will provide updated reports to the DCC as new information becomes available. DCC personnel will review the data and query the clinical sites for clarification and additional information. In addition, the DCC will provide the information to the Data and Safety Monitoring Board (DSMB) as part of their safety review.

The DCC will provide study-wide summary statistics (not filtered by treatment group) of adverse events to the single IRB annually and upon request to all sites on an annual basis for submission to their IRBs.

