**Table 2. Types of Serious Adverse Events and their reporting requirements**

TYPE	SITE	DCC
Unanticipated and related/possibly related SAE, fatal or life-threatening	Report to DCC within 1 business day of discovery	Notify DSMB by end of next business day of receiving site report
Other unanticipated and related/possibly related SAE	Report to DCC within 1 business day of discovery	Notify DSMB 5 business days of receiving site report
Anticipated and related/possibly related SAE	Report to DCC within 5 business days of discovery	Notify DSMB 5 business days of receiving site report
Unrelated SAE (anticipated or unanticipated)	Report to DCC within 10 business days (no more than 3 weeks) of discovery	Notify DSMB within 10 business days (no more than 3 weeks) of receiving site report

Upon receiving notification of an SAE, the DSMB will review it via a closed-session email or conference-call discussion. The DSMB will send a report to the DCC within two weeks; reports for life-threatening SAEs will be submitted in one week. The DSMB report will include: statement indicating what related information the DSMB reviewed; the review date; the DSMB’s assessment of the information reviewed; and the DSMB’s recommendation, if any, for the DCC.

The DCC will then record the DSMB report and disburse. The DCC will forward reportable events to all FRIEND investigators and NIHCD. The Protocol PI will evaluate the frequency and severity of the SAEs and determine if modifications to the protocol and consent form are required. Site PIs will report the SAE to their site IRB according to local IRB requirements. For more information, please see the FRIEND/DSMB Communication Procedure.

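### Section 7.3.5 requires SAE reports only from randomisation, although every woman starts EGCG earlier, at screening; its SAE window should be aligned with Section 7.3.3

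*Combined protocol and SAP*

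**What the plan says.** Section 4.3.3 lists under the screening visit: "All patients to start Green Tea extract at this visit". Under Visit 1, on cycle day 1-5, it lists: "Randomization and dispensation of clomiphene citrate/letrozole". Screening may fall at any time in the preceding cycle, so each woman has a period on EGCG alone before she is randomised. The synopsis (Section 2.4) gives the same order.

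Three sections set safety windows:

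- Section 7.3.3: "Site personnel will record all reportable events with start dates occurring any time after informed consent is obtained", ending for serious events "30 days (for SAEs) after the last day of study participation".
- Section 7.3.4: "Adverse events deemed non-serious will be recorded throughout study participation from the start of study drug", ending one week after the last dose. It adds, with no start date: "Investigators also will notify the medical monitor and DCC within 24 hours after knowledge of a death", and extends this notice to life-threatening events, hospitalisation and disability.
- Section 7.3.5: "All serious adverse events (SAEs) that occur from randomization through thirty days after the last dose of study medication must be reported". This section also holds the SAE form, the site's relatedness and expectedness entries, and the Table 2 deadlines. For an anticipated, related SAE, for example, the site's deadline is "Report to DCC within 5 business days of discovery".

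On a separate point, the DSMB charter attached as Appendix K plans a blinded mid-point look at the pooled pregnancy rate and a check on whether more subjects are needed.

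**The concern.** The lead-in is study-drug exposure in a trial whose stated aim is the pharmacokinetics and hepatic safety of EGCG, and whose results are meant to confirm hepatic safety for the larger FRIEND study. A site that follows 7.3.5 literally need not file an SAE form for a serious event in that period. A site that follows 7.3.3 would at least record it. Both could claim to comply, so handling could differ across the four sites. It is also odd that the non-serious window opens before the serious one.

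The charter text, taken at face value, asks the DSMB to judge sample size on an outcome that this trial does not measure.

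**Working it through.** The plan states no figure on this point to reproduce. The check is a comparison of texts with a little arithmetic.

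1. Windows side by side.

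| Section | Events | Start | End |
|---|---|---|---|
| 7.3.3 | SAEs | informed consent | 30 days after last day of participation |
| 7.3.3 | non-serious AEs | informed consent | 7 days after last day of participation |
| 7.3.4 | non-serious AEs | start of study drug | one week after last dose |
| 7.3.5 | SAEs | randomisation | 30 days after last dose (6 weeks after delivery if pregnant) |

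The order of events in 4.3.3 is consent, first EGCG dose, randomisation. Of these windows, only that of 7.3.5 opens after EGCG exposure has begun.

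2. Which lead-in SAEs have another expedited route. Section 7.3.1.2 counts as serious: death, life-threatening events, hospitalisation, incapacity, congenital anomaly and important medical events.

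- Death, life-threatening events, hospitalisation and disability: 24-hour notice under 7.3.4.
- SAEs that are unanticipated problems: 7.4.2 applies the Table 2 timeline, with no randomisation limit.
- Liver toxicity: 4.3.6 sends all reports to the DSMB, with no start date, but also with no deadline of its own.
- Left over: mainly SAEs that are serious only as important medical events and are neither unanticipated problems nor liver toxicity.

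3. What the leftover class loses. After randomisation, Table 2 allows 5 + 5 = 10 business days from site discovery to DSMB notice for an anticipated, related SAE, and 10 + 10 = 20 for an unrelated one. Before randomisation, 7.3.5 sets no deadline. What remains is documentation under 7.3.3, data entry within three weeks of the visit (7.5.1) and the SAE listing in the DSMB reports.

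4. End of the window. The difference between the two end points is the day of last participation minus the day of last dose. If the last dose is at Visit 1 (day 1-5) and participation ends at Visit 4 (day 30-35), it is 30 - 5 = 25 to 35 - 1 = 34 days. If the last dose is at Visit 2 (day 8-10), it is 30 - 10 = 20 to 35 - 8 = 27 days. Most of this lies after Visit 4. With a last dose at Visit 1, 7.3.5 closes on day 31-35, so at most 35 - 31 = 4 days of participation are uncovered. With a last dose at Visit 2 it closes on day 38-40, and none are.

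5. Share of exposure in the lead-in (illustrative only). Assumptions: cycle length L; screening equally likely on each day s = 1 to L; Visit 1 on day v1 = 1 to 5 of the next cycle; Visit 4 on day v4 = 30 to 35; daily EGCG to Visit 4; 2 months taken as 60 days, with longer paths dropped. Share = (L - s + v1) / (L - s + v4). For example, with L = 28, s = 14, v1 = 3 and v4 = 32, the share is 17/46 = 37%. Averaged over all permitted combinations, the mean share is 29% for L = 21, 34% for L = 28 and 34% for L = 35. The minimum is 1/35 = 3% in each case; the maxima are 25/50 = 50%, 32/57 = 56% and 35/60 = 58%.

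6. Charter interim. The trial is open-label (5.1), requires double-barrier contraception (4.3.4) and has no pregnancy outcome (2.5, 2.6). If the mid-point is taken as 18 of 36 women, the charter's predicted rate of 30-40% would mean 0.30 × 18 = 5.4 to 0.40 × 18 = 7.2 pregnancies, which cannot be the expectation here.

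**The case against.** The best defence is that little escapes. Section 7.3.3 requires all AEs on study to be documented. Both the brief and the full DSMB reports list serious adverse events with no randomisation limit, and the board meets quarterly. The single-IRB notice in 7.3.5 is triggered by the DCC's knowledge of an SAE, so it can follow a 24-hour notice under 7.3.4. Even the obvious candidate for a missed event, gastrointestinal upset judged serious without admission, may be caught: an event can be unexpected by its severity, so 7.4.2 might apply. This largely stands. A reader might infer that lead-in SAEs would go unreported; the documents do not support that.

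A second defence is that 7.3.3 governs recording and 7.3.5 expedited reporting, and that reportable events in 7.3.3 may mean those that 7.3.5 makes reportable. That reading is possible. It turns a contradiction into an ambiguity, but it leaves the consent start in 7.3.3 without effect for lead-in SAEs, so the passages still need aligning.

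Two figures also invite over-reading. The 25-34 days might be taken as a hole in follow-up during participation, but at most 4 of those days precede Visit 4. The exposure shares might be taken as the proportion of events missed or of liver risk. They are neither: they rest on assumed cycle lengths, and 4.4.2 places liver toxicity mainly after 3-4 months of use.

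On the charter, its text is written for the FRIEND study, the name that Sections 3.1 and 5.2 give to the larger trial, and some charter pages are not in the text reviewed. A reader might infer that a pregnancy interim is really planned here, or that no statement of applicability exists; neither can be shown. Against that, Section 7.7 attaches the charter to this protocol, and its reference to three groups matches this trial's three arms.

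**Conclusion.** The point holds on the text alone: 7.3.5 starts SAE reporting after EGCG exposure begins, out of line with 7.3.3 and later than the non-serious window in 7.3.4. The practical gap is narrow. It is mainly the loss of the SAE form and of the 10- or 20-business-day route for lead-in SAEs that are serious only as important medical events and have no other expedited route. No count of affected events can be given. The different end points are a lesser inconsistency that bears on women who stop treatment and stay in follow-up, as 4.3.6 provides. None of this affects the pharmacokinetic comparison, the sample size or the liver termination rule. It should be fixed because hepatic safety is a stated aim and the correction costs almost nothing. The charter interim is a minor mismatch.

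**What to change.** In 7.3.5, replace the randomisation start with informed consent, to match 7.3.3, or at the latest with the first EGCG dose. State one SAE start point and one SAE end point in both 7.3.3 and 7.3.5, and say whether reportable events in 7.3.3 has its own meaning or refers to 7.3.5. In Appendix K, add a sentence that the pregnancy-rate interim and its sample-size check do not apply to this trial.

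The cost is a short wording amendment and possibly a few more SAE forms. No new visits, samples or data items are needed.

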##### 7.3.1.2 Definition of Serious Adverse Events (SAE)

An adverse event (AE) or suspected adverse reaction is considered "serious" if, in the view of either the investigator or sponsor, it results in any of the following outcomes: death, a life-threatening adverse event, inpatient hospitalization or prolongation of existing hospitalization, a persistent or significant incapacity or substantial disruption of the ability to conduct normal life functions, or a congenital anomaly/birth defect. Important medical events that may not result in death, be life-threatening, or require hospitalization may be considered serious when, based upon appropriate medical judgment, they may jeopardize the participant and may require medical or surgical intervention to prevent one of the outcomes listed in this definition.

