## **7.5 Data Collection and Management (including quality assurance/compliance measures)**

### *7.5.1 Data Entry and Forms*

Case Report Forms (CRFs) will be developed as the protocol is developed. All CRFs will be paper forms. Site coordinators will be responsible for timely CRF completion and data entry of the CRFs into the designated electronic data entry (EDC) system. CRF completion should occur at the time of the visit. Lab results sections should be completed within two weeks of results. Each site is asked to ensure that all data is entered into the EDC system within three weeks of the study visit.

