## 9 Appendix K: DSMB Charter

### DATA AND SAFETY MONITORING BOARD (DSMB) CHARTER

#### Purpose and Responsibilities of the DSMB

The members of the Data and Safety Monitoring Board (DSMB) identified in this Charter for the FRIEND study are responsible for safeguarding the interests of study participants, assessing the safety and efficacy of all study procedures, and shall monitor the overall conduct of the FRIEND trial. This Committee will serve as an independent advisory group to the Director of NICHD, and is required to provide recommendations about starting, continuing, and stopping the FRIEND study.

This Committee is responsible for identifying mechanisms to complete various tasks that will impact the safety and efficacy of all study procedures, and overall conduct. The table below identifies the key areas where oversight is necessary and the ways in which the Committee for the FRIEND study will complete those tasks.

Basic Responsibility of DSMB	Method DSMB for FRIEND will use to complete task
Familiarize themselves with the study protocol	
 
Review study protocols and informed consent forms.
 

Monitor adverse events	
 
Adverse Event: Review quarterly progress reports prepared by the DCC.
 
Serious Adverse Events: Review report submitted by the DCC within one week of the event if life-threatening or fatal, or within two weeks otherwise.
 
The DSMB will submit a report of their review to the DCC Coordinator within 7 business days if the SAE is life-threatening or fatal, or within two weeks otherwise.
 

Monitor data quality	
 
Conduct interim evaluations of the data.
 

Oversee participant recruitment and enrollment	
 
Review interim progress reports prepared by the DCC.
 

Develop an understanding of the Study's risks and benefits	
 
Review study protocols and related literatures.
 
Review interim reports of subject accrual and outcome measures provided by the DCC.
 
Assess the need to perform further in-depth evaluation of the benefits and risks of the study after reviewing each report.
 

Ensure the proper reporting occurs	
 
Review and approve the meeting and reporting schedule listed in Sections 5 and 6 of this DSMB charter.
 

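### Section 7.3.5 starts mandatory SAE reporting at randomization, although every woman starts EGCG at screening, up to about one cycle earlier

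*Combined protocol and SAP*

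**What the plan says.** Sections 2.4 and 4.3.3 have every woman begin EGCG from the screening visit, which may fall anywhere in cycle 1. Assignment to EGCG alone, with clomiphene or with letrozole happens at Visit 1, on cycle day 3 ± 2.

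Three neighboring safety sections give three start dates:

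- Section 7.3.3, for recording reportable events: "start dates occurring any time after informed consent is obtained".
- Section 7.3.4, for recording non-serious events and reporting them to the DCC: "from the start of study drug through one week after the last dose of study medication".
- Section 7.3.5, for mandatory SAE reporting: "All serious adverse events (SAEs) that occur from randomization through thirty days after the last dose of study medication must be reported". The SAE form and the Table 2 deadlines belong to this section.

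Other provisions have no randomization start. Section 7.3.4 adds: "Investigators also will notify the medical monitor and DCC within 24 hours after knowledge of a death". The same sentence covers life-threatening events, hospitalization and disability. Section 7.4.2 puts SAEs that are unanticipated problems on the Table 2 timeline. Section 4.3.6 has the DSMB review all liver toxicity reports.

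For the results, sections 2.7 and 6.4 present liver changes for the three treatment groups, with further breakdown by age group and fibroid status. No population of all EGCG-exposed women is defined.

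**The concern.** Hepatic safety is part of the primary aim (section 4.1), and section 5.2 says the results will be used to confirm hepatic safety for the larger FRIEND study. The agent under suspicion is EGCG, and every woman takes it before she is randomized. A mandatory SAE window that opens at randomization therefore leaves out the first stretch of exposure. The window closes by reference to drug exposure (thirty days after the last dose) but does not open by reference to it.

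Read literally, a non-serious lead-in event must go to the DCC, while a serious one does not trigger the SAE form. Sites have two start dates for the same SAE, and a site that follows 7.3.5 would be acting within the protocol.

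A smaller, related matter is that a woman who takes EGCG and leaves before assignment belongs to none of the three groups, so the planned liver tables do not show her.

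**Working it through.** **1. Length of the lead-in.** From section 4.3.3: screening on any day of cycle 1, Visit 1 on cycle day v = 1 to 5, Visit 4 on day 30 to 35. Assumptions: cycle length L = 28 days, screening equally likely on each day s = 1 to 28, and EGCG taken until Visit 4.

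Lead-in = L − s + v.

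- v = 1: 1 to 28 days, mean 14.5
- v = 3: 3 to 30 days, mean 16.5
- v = 5: 5 to 32 days, mean 18.5

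For cycles of 24 to 35 days the extremes are 24 − 24 + 1 = 1 day and 35 − 1 + 5 = 39 days.

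Share of EGCG days before randomization = mean lead-in / (mean lead-in + Visit 4 day − v).

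- Central: 16.5 / (16.5 + 32.5 − 3) = 16.5 / 46 = 0.36
- Low: 14.5 / (14.5 + 35 − 1) = 14.5 / 48.5 = 0.30
- High: 18.5 / (18.5 + 30 − 5) = 18.5 / 43.5 = 0.43

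**2. Which lead-in SAEs are covered elsewhere.** Going through the SAE definition in 7.3.1.2:

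- Death, life-threatening event, hospitalization, disability: 24-hour notice to the medical monitor and DCC (7.3.4).
- Any SAE that is an unanticipated problem (unexpected, related or possibly related, and suggesting greater risk; 7.4.1): Table 2 timeline through 7.4.2. For unanticipated, related SAEs the site step in Table 2 is "Report to DCC within 1 business day of discovery".
- Liver toxicity of any grade: DSMB review (4.3.6), with no deadline given.
- The remaining class in 7.3.1.2: "Important medical events that may not result in death, be life-threatening, or require hospitalization may be considered serious". The 24-hour list omits it. If such an event is also not an unanticipated problem, no SAE timeline reaches it before randomization.

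An example is an outpatient transaminase rise that the investigator judges serious. Section 4.4.2 lists transaminase elevation and rare liver toxicity as EGCG risks, so it may well be classed as anticipated.

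**3. Timing for that residual event.**

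- After randomization (Table 2, anticipated and related): 5 business days from discovery to the DCC, then 5 to the DSMB, so 5 + 5 = 10.
- Before randomization (7.5.1): laboratory sections of the form within two weeks of results, and for entry: "Each site is asked to ensure that all data is entered into the EDC system within three weeks of the study visit". Three weeks is about 3 × 5 = 15 business days to reach the database, with no stated deadline for the step to the DSMB.

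The clocks start at different points (discovery, result, visit), so this is a comparison of stated limits and not a measured delay.

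**4. Liver results.** The documents do not say how many women will be dosed but not randomized. For scale only: one liver event among 36 randomized women is 1/36 = 2.8%. Adding one dosed, unrandomized woman gives 1/37 = 2.7% if she had no event and 2/37 = 5.4% if she had one.

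**The case against.** The strongest reply is that 7.3.5 is an isolated wording slip and that other sections keep the DCC and DSMB informed. Much of this stands, and it rules out several stronger readings.

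- A reader might infer that lead-in SAEs go unreported, or that 36% of exposure is unmonitored. The documents do not support that. Recording starts at consent, the gravest categories carry 24-hour notice, and SAEs that are unanticipated problems follow Table 2. Nor is 36% of days 36% of the risk: section 4.4.2 says toxicity appears mainly after 3–4 months of use.
- A reader might infer that data entry within three weeks is the only site timeline for any non-hospitalized lead-in SAE, including an unanticipated and related one. Section 7.4.2 normally covers that case, so the gap is confined to events outside the unanticipated-problem definition.
- A reader might point to the DSMB charter: "Review report submitted by the DCC within one week of the event if life-threatening or fatal, or within two weeks otherwise". Missing that limit is not peculiar to the lead-in, because Table 2 itself allows 10 + 10 business days for unrelated SAEs.
- A reader might infer that a woman with a high Visit 1 liver value drops out of the liver tables. The sample and the randomization share that visit, and nothing holds assignment until the result is known, so she may well be randomized first. An unscheduled earlier test is the clearer route.
- Section 7.3.4 already provides adverse event statistics not filtered by treatment group, and full DSMB reports give numbers screened beside numbers enrolled. The charter defines enrolled as randomized, but it is weak evidence about this study's tables: its planned interim look at pregnancy rates belongs to the larger trial.

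The objection does not remove the conflict between 7.3.3, 7.3.4 and 7.3.5, or the residual class of event.

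**Conclusion.** The concern holds in a limited form. Section 7.3.5 contradicts the two sections before it and, as worded, leaves on-drug SAEs outside the SAE form and its deadlines for up to about one cycle; for a woman never randomized this is permanent. After allowing for the other provisions, the practical gap is non-hospitalized important medical events in the lead-in that are not unanticipated problems. Few such events are likely in a study of 36 women, but a serious yet anticipated liver enzyme rise is among them, and that matters in a hepatic safety study. The change should be made because it is specific and nearly free.

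The lead-in lengths and shares rest on the assumed cycle length and uniform screening day. That the example would be classed as anticipated is a judgment left to investigators.

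The missing summary of all dosed women is a minor reporting point. The number affected is unknown, the between-arm comparison is unaffected, and the overall liver-event rate could move slightly either way.

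**What to change.** 1. In 7.3.5, start the SAE window at informed consent, matching 7.3.3, or at the first EGCG dose. This brings the SAE form and Table 2 deadlines into force for the lead-in and for women never randomized. The cost is one wording change and a few more SAE reports.
2. Minor: in 2.7 and 6.4, add one descriptive line or table of all women who took at least one EGCG dose, giving the number dosed but not randomized, the reasons, and any adverse events or on-drug liver values already collected. The first scheduled on-drug liver test is at Visit 1, so for women who leave earlier this will mostly be counts, reasons and events. No extra liver panel is needed, and the arms, sample size and between-arm analysis stay as they are.
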